MEDICAL PROTOCOL (HRP-590)

PROTOCOL TITLE: Comparison of normothermia maintenance between resistive blanket and forced air warming systems in renal transplant surgery

VERSION DATE: V43 January June 6, 2022

ANCILLARY REVIEWS

Which ancillary reviews do I need and when do I need them? Refer to HRP-309 for more information about these ancillary reviews.			
Select yes or no	Does your study...	If yes...	Impact on IRB Review
 Yes  No	Include Gillette resources, staff or locations	Gillette Scientific review and Gillette Research Administration approval is required. Contact: [contact]	Required prior to IRB submission
 Yes  No	Involve Epic, or Fairview patients, staff, locations, or resources?	The Fairview ancillary review will be assigned to your study by IRB staff Contact: [contact]	Approval must be received prior to IRB committee/designated review.
 Yes  No	Include evaluation of drugs, devices, biologics, tobacco, or dietary supplements or data subject to FDA inspection?	The regulatory ancillary review will be assigned to your study by IRB staff Contact: [contact] See: https://policy.umn.edu/research/indide	Consider seeking approval prior to IRB submission.
 Yes  No	Require Scientific Review? Not sure? See guidance on next page.	Documentation of scientific merit must be provided. Contact: [contact]	
 Yes  No	Relate to cancer patients, cancer treatments, cancer screening/prevention, or tobacco?	Complete the CPRC application process. Contact: [contact]	
 Yes  No	Include the use of radiation? (x-ray imaging, radiopharmaceuticals, external beam or brachytherapy)	Complete the AURPC Human Use Application and follow instructions on the form for submission to the AURPC committee. Contact: [contact]	Approval from these committees must be received prior to IRB approval;
 Yes  No	Use the Center for Magnetic Resonance Research (CMRR) as a study location?	Complete the CMRR pre-IRB ancillary review Contact: [contact]	
 Yes  No	Include the use of recombinant or synthetic nucleic acids, toxins, or infectious agents?	Complete the IBC application via eprotocol.umn.edu Contact:	These groups each have their own application process.
 Yes  No	Include the use of human fetal tissue, human embryos, or embryonic stem cells?	Contact OBAO for submission instructions and guidance	

MEDICAL PROTOCOL (HRP-590)

PROTOCOL TITLE: Comparison of normothermia maintenance between resistive blanket and forced air warming systems in renal transplant surgery

VERSION DATE: V43 January June 6, 2022

 Yes  No	Include PHI or are you requesting a HIPAA waiver?	If yes, HIPCO will conduct a review of this protocol. Contact: [contact]	
 Yes  No	Use data from the Information Exchange (IE)?	The Information Exchange ancillary review will be assigned to your study by IRB staff Contact: [contact]	Approval must be received prior to IRB approval.
 Yes  No	Use the Biorepository and Laboratory Services to collect tissue for research?	The BLS ancillary review will be assigned to your study by IRB staff. Contact: [contact]	
 Yes  No	Have a PI or study team member with a conflict of interest?	The Col ancillary review will be assigned to your study by IRB staff Contact: [contact]	
 Yes  No	Need to be registered on clinicaltrials.gov?	If you select "No" in ETHOS, the clinicaltrials.gov ancillary review will be assigned to your study by IRB staff Contact: [contact]	These groups do not have a separate application process but additional information from the study team may be required.
 Yes  No	Require registration in OnCore?	If you select "No" or "I Don't Know" in ETHOS, the OnCore ancillary review will be assigned to your study by IRB staff Contact: [contact]	Does not affect IRB approval.

MEDICAL PROTOCOL (HRP-590)

PROTOCOL TITLE: Comparison of normothermia maintenance between resistive blanket and forced air warming systems in renal transplant surgery

VERSION DATE: V43 JanuaryJune 6, 2022

VERSION DATE: V43 January June 6, 2022

ABBREVIATIONS/DEFINITIONS

FA: Forced air [warming system]

RB: Resistive blanket [warming system]

ESRD: end stage renal disease

PA: Pulmonary artery

ICU: Intensive care unit

OR: Operating room

PACU: Post-anesthesia care unit

CRNA: Certified registered nurse anesthetist

NP: Nasopharyngeal

AUC: area under the curve. In this study, the area under the curve is defined as the cumulative summation of the change in temperature from T_i multiplied by the time interval between temperature samplings. This gives a surrogate measurement in effectiveness in maintaining body temperature

DSMB: Date and safety monitoring board

MEDICAL PROTOCOL (HRP-590)

PROTOCOL TITLE: Comparison of normothermia maintenance between resistive blanket and forced air warming systems in renal transplant surgery

VERSION DATE: V43 JanuaryJune 6, 2022

1.0 Objectives

1.1 Purpose:

The purpose of the study is to compare the effectiveness of resistive blanket warming to forced air warming in maintaining body temperature in patients undergoing renal transplantation.

Secondary outcome variables also include:

- AUC of time versus temperature curves
- temperatures at set points during operative period
- Blood loss volumes

2.0 Background

2.1 Significance of Research Question/Purpose:

Patients undergoing general anesthesia are less able to maintain body temperature compared to the awake state due to several factors: 1) Warmer blood normally kept in the torso of the body and organs moves to the limbs and to the skin, where heat is lost more easily to the environment through a cold operating room, moisture evaporation, and heat loss from the patient through heat radiation; 2) The patient is also unable to maintain body temperature since shivering is reduced or abolished. Reduced body temperatures can result in blood being unable to clot appropriately in extreme circumstances, which leads to increased blood loss. The immune system function is also impaired, which results in increased infection rates. Shivering after general anesthesia to increase body temperature also increases oxygen demand of the body, which can also cause increased work of the heart, leading to heart injury. [1,2] For all of these reasons, body temperature is continuously monitored and efforts to maintain body temperature during surgery are a standard of care.

The mainstay of maintaining patient body temperature in the operating room is through active warming techniques, using conductive or convective heat transfer via specially designed blankets. Conductive warming systems work by transferring heat directly through skin contact with an electric blanket or a blanket with circulating warm water. Convective warming continuously circulates warm air at the surface of the skin through air conduits through a blanket that has small holes where the air escapes through. Typically, this forced air warming system (FAWS) is only able to warm the patient in areas where the warm air is constantly refreshed through convective air currents. [3] Areas of the skin that are in contact with the bed or above sterile drapes are not able to be warmed, since warm air cannot circulate to those regions, and becomes a particular challenge with patients who undergo cardiac surgery, since the amount of body surface area available for warming is much lower compared to other surgeries.

MEDICAL PROTOCOL (HRP-590)

PROTOCOL TITLE: Comparison of normothermia maintenance between resistive blanket and forced air warming systems in renal transplant surgery

VERSION DATE: V43 January June 6, 2022

2.2 Preliminary Data:

None

2.3 Existing Literature:

Few studies have been done with comparing thermoregulation during prolonged transplant surgeries between different types of warming devices. One quality improvement project showed increased core temperature at ICU handoff for TAVR and open cardiac surgeries with a water-circulation device. [6] FAWS available include upper body, lower body, or under body, however we are interested in investigating whether the resistive blanket warming system (RBWS) may heat more evenly across the surface area and thereby offer advantages over FAWSs.

3.0 Study Endpoints/Events/Outcomes

3.1 Primary Endpoint/Event/Outcome:

Patient temperature at the end of surgery.

3.2 Secondary Endpoint(s)/Event(s)/Outcome(s):

- AUC of temperature vs time curve during hypothermia (core temperature less than 36°C) during the duration of surgery

Time during surgery spent under 36 degrees through comparison of nasopharyngeal temperature, which is measured by placing a nasopharyngeal temperature probe 10 to 20 cm into the nare (standard of care) [8], between FAWS and RBWS. The study will be conducted as a superiority trial where a 0.5°C difference between the FAWS and RBWS is considered to be significant.

- Minimum body temperature upon arrival in PACU
- Maximum body temperature difference (maximum temperature minus minimum temperature) upon arrival in PACU
- First temperature upon arrive in PACU, last temperature (temperature time weighted average)
- Requiring rescue intervention which will be turning on a second, upper body warming blanket if the temperature is consistently below 35.5 degrees

4.0 Study Intervention(s)/Investigational Agent(s)

4.1 Description:

Forced air warming system (Bair Hugger, Model 635; 3M Medical, St. Paul, MN, USA)

The forced air warming system has a heater unit that blows air through a conduit to an “air blanket” that inflates with forced air that circulates throughout the

MEDICAL PROTOCOL (HRP-590)

PROTOCOL TITLE: Comparison of normothermia maintenance between resistive blanket and forced air warming systems in renal transplant surgery

VERSION DATE: V43 January June 6, 2022

blanket, and exits through tiny perforations on the patient-side of that blanket. The heat primarily warms the subject through convective means. As the warmed air escapes through the perforations in the blanket, it creates an environment of continuously circulating warm air that is in contact with the skin. Note, however, that warmed air is only able to move over the skin surface in areas of the body that are immediately adjacent to the blanket and which are not compressing the blanket (and hence blocking airflow). In many surgical cases, the FAWS is placed above the patient so a very large fraction of the patient's skin area is exposed to warm air. Air blankets are placed under the patient by some providers in transplant cases, however, which then results in the blanket conduits then being collapsed/occluded by the weight of the patient - and warm air can circulate only under a small fraction of the patient's upper torso and legs.

The Bair Hugger blanket is the standard of care and will be billed as usual to insurance.

Resistive blanket warming system (Hotdog (U102); Augustine Surgical, Inc., Eden Prairie, MN, USA)

This blanket is equivalent to an operating-room-safe electric blanket. Through a power cord, a separate power source powers a semiconductor layer within the resistive blanket to generate heat. The heat primarily warms the subject by conductive warming through direct skin contact, and, secondarily, by warming the air around the participant in areas where there is no direct skin contact.

The participant will be placed on either the underbody FAWS or the RBWS on the operating room table depending on which device the patient is randomized to, this will then be the main warming device during the surgery. The main warming device will be turned on once the patient is positioned on the operating table.

An additional upper body FAWS will be placed on top of the patient prior to surgery for rescue purpose and will only be utilized if normothermia cannot be achieved during the surgery with the device the patient is randomized to. During periods when the participant will need to be warmed, the additional upper body device will be switched on to generate heat in addition to the main warming device.

The Hotdog blanket will be donated by the manufacturer. The Anesthesiologist will train CRNA staff on the use of this device and will maintain continual communication with the CRNA Lead to ensure staff is aware of the study and receives proper training. A staff member from the Anesthesiology Research Office will be in charge of the inventory of the donated blankets, stored in the core of the OR department. A research team member will bring the Hotdog device to the OR prior to surgery, if the patient is randomized to Hotdog and will make sure there is a rescue Bairhugger in the OR for all patients. After the surgery, OR staff

MEDICAL PROTOCOL (HRP-590)

PROTOCOL TITLE: Comparison of normothermia maintenance between resistive blanket and forced air warming systems in renal transplant surgery

VERSION DATE: V43 January June 6, 2022

will do their normal process of cleaning supplies, including the Hotdog, and will put the device back in the OR core.

The HotDog resistive blanket warming system is FDA approved and available for use in surgery.

4.2 Device Handling:

During the study, the participant will be randomized to lay on top of either the underbody forced air warming system or resistive blanket, this will be the main warming device for the patient. An additional upper body device will be placed on patients in case rescue warming is needed at the discretion of the anesthesiologist. All staff participating in patient care will be instructed that a patient's body temperature of 35.5 degrees Celsius or lower is the threshold for intervention. During periods when the participant will need to be warmed, the additional upper body device will be switched on to generate heat in addition to the main warming device.

Forced air warming blankets are single patient use only. The resistive blankets are reusable. In between use, the resistive blankets will be cleaned and disinfected per manufacturer's instructions.

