4.3 Biosafety: N/A

4.4 Stem Cells: N/A

4.5 Fetal Tissue: N/A

5.0 Procedures Involved

5.1 Study Design:

Single institution, prospective, randomized, unblinded superiority study of renal transplant surgery participants, with no history of previous transplant, comparing a resistive blanket warming system (Hotdog (U102); Augustine Surgical, Inc., Eden Prairie, MN, USA) to a forced air warming system (Bair Hugger, Model 635; 3M Medical, St. Paul, MN, USA).

A randomization schedule will be developed using permuted block randomization with blocks of size 2, 4, 6, and 8 assuming 1:1 allocation within each block. Data will be analyzed using an intention-to-treat protocol.

5.2 Study Procedures:

The study will involve two arms: a resistive blanket warming system arm and a forced air warming system arm. Both devices will be set to warm the patient at each device's maximum setting at the beginning and throughout the case. The hotdog's maximum setting is 39C and the Bair Hugger's maximum setting is 41C.

The patient will be randomized to either the FAWS or RBWS before arrival to the operating room. Depending on which arm they have randomized to, the

MEDICAL PROTOCOL (HRP-590)

PROTOCOL TITLE: Comparison of normothermia maintenance between resistive blanket and forced air warming systems in renal transplant surgery

VERSION DATE: V43 January June 6, 2022

participant will be placed on either the underbody FAWS or the RBWS. An upper body FAWS will be placed on top of the patient prior to incision but is only to be utilized if normothermia cannot be achieved during the surgery with either device. The warming system that the patient is randomized to will be set up on the table before the participant is brought to the OR and transferred to the operating room table. The main warming device will be turned on once the patient is positioned on the operating table. The CRNA's will be involved in the placement of the blankets. Surgeons, OR Nurse Managers, and CRNA's will be informed by research team regarding patient's involvement in the study.

After the needed standard monitors for surgery have been placed, general anesthesia will be induced and maintained with patient's hemodynamics and other vitals maintained per standard care (no additional measurements beyond standard of care which is recorded in EPIC). Standard anesthetic care of the participant will occur for the duration of the surgery.

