Patient core temperature will be measured with a nasopharyngeal temperature probe. The patient's temperature will be monitored and recorded for the duration of surgery with the selected warming system. Vital signs, including continuous blood pressure, heart rate, oxygen saturation, and end-tidal carbon dioxide, will be monitored and recorded in Epic as is routine with all anesthetics performed. Our primary outcome variable is the NP temperature as recorded at the end of the surgery.

After the surgery, the patient will be transported to the PACU in a timely fashion. Temperature measurement in the PACU will be standardized with skin temperature probes (3M Spot-On) that will be placed on the forehead prior to leaving the operating room. If there is an unexpected delay in transporting the patient to the PACU, that will be documented and the temperature upon arrival to PACU will not be valid.

Data to be collected about participants and the source records that will be used to collect those data:

From Epic:

- Age
- Sex
- MRN
- Height
- Weight
- BMI
- Date of procedure
- Procedure performed

MEDICAL PROTOCOL (HRP-590)

PROTOCOL TITLE: Comparison of normothermia maintenance between resistive blanket and forced air warming systems in renal transplant surgery

VERSION DATE: V43 January June 6, 2022

- Nasopharyngeal temperature throughout surgery (every minute)
- Time at warming system being switched (resistive blanket or forced air)
- Time when patient reaches 37°C
- Time at OR departure
- Time sign-out from PACU prior to transfer to regular nursing floor
- Blood product volume administered to patient (red blood cells, fresh frozen plasma, platelets, and cryoprecipitate)
- Recorded incidence of rescue warming used for when patient's temperature is at 35.5°C (requiring rescue means the need to turn on the additional forced air warming device that may be due to severe hypothermia and uncontrolled bleeding)

Individually Identifiable Health Information: See above

HIPAA Agreement: Attached

5.3 Study Duration:

Individual Subject Participation Duration: Patients will be in the study for their scheduled procedure and for 1 hour following their procedure. Duration of the surgical procedure, is typically 2-5 hours depending on the surgery required. Following the study, participants will not be approached at any time, for any reason as it pertains to their study participation.

Total Study Duration (all Participants): approximately 1 year

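### The rescue outcome is scored by whether unblinded staff switched on the upper-body blanket, so a difference between arms can partly reflect readiness to act; an arm-blind outcome from the temperature trace should sit beside it

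*Combined protocol and SAP*

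**What the plan says.** **What is counted.** Section 3.2 lists as a secondary endpoint "Requiring rescue intervention which will be turning on a second, upper body warming blanket if the temperature is consistently below 35.5 degrees". Section 15.1 lists rescue warming again among the safety outcomes, to be compared by chi-square or Fisher's exact test and by logistic regression.

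**Who decides, and on what.** Section 4.2 states: "An additional upper body device will be placed on patients in case rescue warming is needed at the discretion of the anesthesiologist". Its next sentence instructs all staff that "a patient's body temperature of 35.5 degrees Celsius or lower is the threshold for intervention". Section 4.1 ties use of the upper-body blanket to a different condition: it "will only be utilized if normothermia cannot be achieved during the surgery with the device the patient is randomized to". Section 5.2 has similar normothermia wording.

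**Blinding.** Section 5.1 describes a "Single institution, prospective, randomized, unblinded superiority study of renal transplant surgery participants".

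**What is recorded.** The data list in 5.2 includes "Nasopharyngeal temperature throughout surgery (every minute"). It also includes "Recorded incidence of rescue warming used for when" the temperature is at 35.5°C, and adds that the need may come from severe hypothermia and uncontrolled bleeding.

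**What is checked.** In 18.1 the PI or co-PI reviews each subject's record, including whether rescue was carried out and carried out correctly. No section scores rescue from the temperature trace, and none provides for blinded adjudication.

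**The concern.** The outcome has two ingredients: how cold the patient became, and whether people who could see the device decided to act. Only the first is a property of the warming system.

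Forced air is the site's standard of care, while staff are to be trained on the resistive blanket for this study. Unequal confidence in the two devices is therefore plausible, although the documents do not report it. If staff act sooner for the device they trust less, the rescue comparison shows a difference that is only behaviour. If they act later, it can hide a real one. The same figure appears in the safety comparison.

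Agreeing on a single trigger would not remove this, because the event counted would still be the act. The minute-by-minute trace already being extracted could show whether the trigger was met, with no one's judgement involved.

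**Working it through.** **Inputs from the documents.** 49 per arm (15.2), 1:1 allocation (5.1), significance at p<0.05 (15.3), chi-square or Fisher for rescue (15.1).

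**Inputs assumed.** The documents give no rescue rate. Let *r* be the share of patients reaching the trigger, the same in both arms, and *a* the share of those in whom staff switch the blanket on.

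**The plan's own figure.** For 0.5°C, SD 0.75, 90% power and two-sided 0.05, the normal approximation gives n = 2(1.960 + 1.282)² × 0.75² / 0.5² = 2 × 10.51 × 2.25 = 47.3, so 48 per group. The two-sample t-test calculation gives 49, with power 0.904. The stated 49 is reproduced. It was set for end-of-surgery temperature and says nothing about rescue.

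**Step 1: observed rates with no difference in warming.** Observed rescue = r × a. With r = 0.40, action rates of 90% and 60% give 0.40 × 0.90 = 36% and 0.40 × 0.60 = 24%.

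**Step 2: rough check.** Pooled rate 0.30; SE = √(0.30 × 0.70 × 2/49) = 0.0926; expected z = 0.12/0.0926 = 1.30. The chance that z exceeds 1.96 is about P(Z > 0.66) = 0.25.

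**Step 3: exact enumeration.** Sum the binomial probabilities of every pair of counts (0 to 49 in each arm) for which p<0.05, using the uncorrected chi-square and Fisher's test.

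| Reaching trigger, both arms | Action rates | Observed rescue | Chi-square | Fisher |
|---|---|---|---|---|
| 40% | 90% vs 90% | 36% vs 36% | 4.8% | 2.9% |
| 40% | 90% vs 80% | 36% vs 32% | 6.7% | 4.4% |
| 40% | 90% vs 70% | 36% vs 28% | 13.2% | 9.3% |
| 40% | 90% vs 60% | 36% vs 24% | 25.1% | 19.1% |
| 20% | 90% vs 80% | 18% vs 16% | 6.2% | 3.0% |
| 20% | 90% vs 60% | 18% vs 12% | 14.0% | 7.5% |
| 60% | 90% vs 60% | 54% vs 36% | 44.7% | 36.7% |

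**Step 4: the same mechanism as earlier action.** Assume the lowest temperature is normal with mean 36.0°C and SD 0.75 in both arms. Suppose staff act at 35.5°C in one arm and 0.3°C sooner in the other. The rates are Φ(−0.5/0.75) = 25.2% and Φ(−0.2/0.75) = 39.5%, and the test is significant in 32% of trials (chi-square) or 25% (Fisher). With a gap of only 0.1°C the figures are about 8% and 5%.

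**Step 5: one rule scored identically.** With the same temperatures and one rule applied by program, both arms have the same expected rate. Rejection returns to about 5% (chi-square) or 3% (Fisher).

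**The case against.** The strongest reply is that the discretion is bounded. The endpoint in 3.2 carries a temperature condition, all staff are told the same 35.5°C threshold, and 18.1 has each record checked for correct use of rescue. All of this stands. A reader might infer that the endpoint ignores temperature altogether, and the documents do not support that. What remains is that the sentence before the threshold grants discretion, *consistently* in 3.2 has no duration, and the 18.1 review neither rescores the outcome nor is said to be blinded.

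A reader might also take the 5.2 data item literally and conclude that activation above 35.5°C goes uncounted. That is one reading only. The same item goes on to describe the need to turn on the device, and 15.1 names rescue warming with no temperature limit. Section 5.2 also lists the time a warming system is switched, which may or may not cover the rescue blanket. The item needs clarifying; it does not show that events are lost.

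Third, time and AUC below 36°C already use temperature over time, and a safety table should report actual rescue use. Both points are fair. They are reasons to keep activation as an outcome and add to it, not to replace it.

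Finally, a trace-based outcome is not fully immune, because early activation can prevent the trigger from being met. That is true and has to be handled explicitly.

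**Conclusion.** The point holds in a limited form. The rescue outcome mixes warming with the readiness of unblinded staff to act, and the plan has no step that separates the two. The threshold instruction and the record review reduce the problem without removing it.

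The size is unknown. A reader might take 25%, or the 44.7% corner of the table, as the expected false-positive rate. The documents support neither: they contain no rescue rate and no sign that staff would act differently by arm. If behaviour differs little (90% versus 80%, with 40% reaching the trigger), the rate is about 7% by chi-square and 4% by Fisher, close to nominal. A gap of 90% versus 60% is needed to reach 25% and 19%.

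Nor does this undermine the primary comparison, which is a measured nasopharyngeal temperature at the end of surgery. Unequal rescue could also shift measured temperatures, because the blanket adds heat, but that is a separate matter that rescoring this outcome would not cure. The point concerns one secondary and safety outcome, and the remedy is cheap.

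**What to change.** 1. **Reconcile the trigger wordings** in 3.2, 4.1, 4.2 and 5.2. Which one applies is the sponsor's choice. For scoring, the agreed wording has to be explicit enough to program, including what *consistently* means if that word stays.
2. **Add a companion outcome in 3.2 and 15.1:** the proportion of patients whose nasopharyngeal trace met that trigger, computed by a program without reference to arm. Use it as the between-arm comparison of need for rescue.
3. **Keep actual activation** of the upper-body blanket as a reported safety and treatment-use outcome.
4. **In 5.2, make clear** that every activation is recorded with on and off times, whatever the temperature.
5. **Add one sensitivity analysis** that counts trigger met or blanket switched on as the event, because early activation can prevent the trigger being met. This brings the discretionary act back in, so it should be read beside the companion outcome and not in place of it.

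The cost is wording in the sections named, one derived variable, the on and off times, and two rescue figures to report instead of one. No patients, procedures or temperature measurements are added, and neither the primary analysis nor the timing of rescue changes.
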